## 8.2. Pharmacokinetic/Pharmacodynamic Relationships

Relationships of PK parameters for JNJ-3989, JNJ-3924, and, optionally, of JNJ-6379, Nas and/or PegIFN- $\alpha$ 2a, as applicable, with selected efficacy and with selected safety endpoints will be evaluated, applying graphical tools and, if feasible, statistical models.

Modeling of key pharmacodynamic parameters (e.g., HBsAg, HBV DNA) may be performed using population pharmacokinetics/pharmacodynamics (PK/PD). Details of the PK/PD analyses will be described in a population PK/PD analysis plan and results will be presented in a separate report.

Effect of PegIFN- $\alpha$ 2a coadministration on the PK of JNJ-3976, JNJ-3924, and JNJ-6379 if applicable, will be presented in a separate report.

## 8.3. Immune Analyses

Descriptive statistics (n, mean, SD, SE, CV, geometric mean, median, minimum, and maximum) may be used to describe the magnitude of the gamma interferon (IFN- $\gamma$ ) T-cell response or the CD4+ and CD8+ T-cell responses (expressing at least 1 cytokine such as interleukin [IL]-2, tumor necrosis factor [TNF]- $\alpha$  or IFN- $\gamma$  specific to any HBV antigen) as defined by ELISpot and/or ICS, respectively. Changes from baseline (if present) may also be tabulated for PBMCs during study intervention and follow-up. The proportion (%) of CHB patients with positive responses based on the magnitude of the IFN- $\gamma$  T-cell response or the CD4+ or CD8+ T-cells expressing at least 1 of the cytokines amongst IL-2, TNF- $\alpha$  or IFN- $\gamma$  for 1 of the HBV antigens as defined by ELISpot and/or ICS, respectively, may be determined. Changes from baseline in HBV-specific peripheral blood T-cell responses may be summarized and tabulated.

Graphs showing the individual subject values as dots, together with horizontal lines indicating the corresponding median and interquartile range (IQR) per time point for each assay may be presented. The spaghetti plots may be used to show the patient profiles per time point for each assay. A graph showing the median and IQR over time by cohort may be presented. A bar chart may be used to show the breadth of response (i.e., HBV-specific immune response rate for combinations of peptide pools).

For intracellular cytokine staining (ICS), for all cytokine combinations (IFNy and/or TNF $\alpha$  and/or IL-2), pie charts may be presented to reflect the distribution of each of the cytokine combinations (i.e., the proportion of a specific cytokine combination of the CD4 or CD8 T-cells secreting at least one cytokine), and bar charts may be presented to reflect the mean magnitude of each combination.

## 9. PATIENT-REPORTED OUTCOMES

The impact of HBV/HDV treatment on participants will be assessed using PROs at predefined time points. The following PRO instruments will be used: Hepatitis B Quality of Life (HBQOL), Short Form 36 version 2 (SF-36), and EQ-5D-5L. All PRO analyses will be performed using the ITT analysis set.

## 9.1. Hepatitis B Quality of Life Instrument (HBQOL)

### 9.1.1. Definition

The HBQOL version 1 is a 31-item disease-specific instrument designed to measure HRQoL for participants with CHB.

Each item is scored on a 5-level response scale ranging from 1 through 5. Each response is transformed along a 0 to 100-point scale, where lower scores denote less HRQoL impact, and higher scores denote more HRQoL impact (i.e., 0=best score; 100=worst score), as follows:

- Level 1 – 0 points
- Level 2 – 25 points
- Level 3 – 50 points
- Level 4 – 75 points
- Level 5 – 100 points

The items are combined to form 7 subscales, as follows:

**Psychological Well-Being (8 Items):** Anxious (F6), Frustrated (F4), Sad (F3), Angry (F7), Less Enjoyable (F10), Scared (F13), Bad (F9), Isolated (F8)

**Anticipation Anxiety (6 Items):** Concern Failure (C1), Concern Cancer (C2), Concern Worsen (C15), Concern Serious (C12), Concern Survival (C9), Concern Flare (C5)

**Vitality (5 Items):** Tiredness (P1), Worn Out (F5), Muscle Aches (P3), Memory Problems (P2), Unproductive (F12)

**Stigma (6 Items):** Concern Embarrassed (C14), Ashamed (F1), Concern Self-Conscious (C10), Concern Socially Isolated (C11), Concern Boss (C3), Stigmatized (F2)

**Vulnerability (3 Items):** Concern Eat (C13), Concern Sick Easily (C6), Concern Medicines (C8)

**Transmission (3 Items):** Concern Transmit Sex (C7), Concern Transmit Child (C4), Sex Difficult (F11)

**Viral Response (4 Items):** Concern Transmit Sex (C7), Concern Transmit Child (C4), Concern Eat (C13), Concern Medicines (C8)

Each subscale score is simply calculated as the average score among the items included in that subscale. In addition to the 7 subscales, there is a single global score that reflects the results on all 31 items. The global score is the average score among all the items in the HBQOL. Responses are transformed along a 0 to 100-point scale, where lower scores denote less HRQoL impact, and higher scores denote more HRQoL impact (i.e., 0=best score; 100=worst score).

For example, consider these sample scores for items in the vulnerability scale:

Item Number	Item Name	Raw Score	Scaled Score
C13	Concern eat	2	25
C6	Concern sick easily	4	75
C8	Concern medicines	3	50
		Average	50

The score on this subscale is 50 out of a possible score of 100, where higher scores denote more severe negative impact of HBV on HRQOL.

### 9.1.2. Analysis Methods

Descriptive statistics of the actual values and change from baseline values at each timepoint (including baseline, Week 24, end of induction, end of consolidation phase, FU Week 24 and FU Week48) for the derived scores will be displayed for subscales/domains and global score by analysis phase and by cohort. The proportion of participants experiencing a clinically important improvement or worsening from baseline (if applicable) at each timepoint will be calculated by analysis phase and by cohort. Clinically important improvement = change from baseline  $\geq 10$ , Clinically important worsening = change from baseline  $\leq -10$ . Other change from baseline values will be categorized as 'No clinically important change'. Analyses will also be performed on the changes from baseline at specific time points (end of consolidation phase, FU Week 24 and FU Week 48) as appropriate for different subgroups: participants with HBsAg seroclearance 24 weeks and 48 weeks after completion of consolidation phase treatment, in patients stopping NA (at FU Week 2) without restarting NA treatment, versus those without HBsAg seroclearance at those time points.

## 9.2. Short Form 36 version 2

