# Hepatitis B Quality of Life Instrument, Version 1.0

The HBQOL version 1 is a 31-item disease-specific instrument designed to measure HRQoL for participants with CHB. The instrument includes 7 subscales/domains, including psychological well-being, anticipation anxiety, vitality, stigma, vulnerability, transmission, and viral response. Each of the 31 items is scored on a 5-level response scale. Each subscale score is simply calculated as the average score among the items included in that subscale. In addition to the 7 subscales, there is a single global score that reflects the results on all 31 items. The global score is the average score among all the items in the HBQOL. Responses are transformed along a 0 to 100-point scale, where lower scores denote less HRQoL impact, and higher scores denote more HRQoL impact (ie, 0 best score; 100 worst score).

It takes about 10 minutes to complete the HBQOL version 1.

See Section 10.11, Appendix 11, Hepatitis B Quality of Life Instrument for a representative example of the HBQOL version 1.

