### **5.3.1.2. Values and Changes Over Time Endpoints**

#### **5.3.1.2.1. HBsAg, HBeAg, HBV DNA and ALT**

Actual values (original unit and  $\log_{10}$  transformed values) and changes from baseline ( $\log_{10}$  transformed values) over time in HBsAg, HBeAg (for participants HBeAg positive at baseline only), HBV DNA and ALT (actual values only) will be evaluated.

Change from baseline is defined as follows: value at a given time point minus baseline value.

The change from baseline value to nadir (i.e., maximum decrease for each participant) in HBsAg, HBeAg and HBV DNA will be evaluated at three intervals: on-treatment nadir, during follow-up nadir, and entire study duration nadir.

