### 9.2.1. Definition

The SF-36 is a 36-item generic PRO instrument designed to measure physical and mental health status. Participants self-report on items that have between 2-6 response options per item using Likert-type responses (e.g., none of the time, some of the time). The SF-36 is scored and interpreted using two summary scores – Physical Component Summary (PCS) and Mental Component Summary (MCS) – and eight domain subscales:

- PF: Physical functioning
- RP: Role limitations due to physical health problems
- BP: Bodily pain
- SF: Social functioning
- MH: General mental health, covering psychological distress & well-being
- RE: Role limitations due to emotional problems
- VT: Vitality, energy and fatigue
- GH: General health perceptions

Although SF-36v2 PCS and MCS scores include information from all 8 SF-36 domain subscales, the PCS score gives more weight to physical aspects of health status as represented in the Physical functioning, Physical role limitations, Pain, and General health perception domain scores. The MCS score gives more weight to the emotional and mental and social aspects of health status as assessed by the Vitality, Social function, Social role limitations, and Mental health domain scores.

A scoring algorithm will be used to convert the raw scores into the eight dimensions listed above. The total domain scores of domain scales will be transformed into a range from zero where the respondent has the worst possible health to 100 where the respondent is in the best possible health. The scores (0-100) will then be standardized using means and standard deviation from 2009 U.S. general population and converted to norm-based scores using a T-score transformation (mean = 50, SD = 10). The two component scores will be derived as linear combination of the standardized (2009 U.S. norm) scores using weights from principal component analysis. Each component score will be transformed to the corresponding PCS T-score and MCS T-score (mean = 50 and SD = 10)

The domain scale scores, and component summary scores will be calculated using the Quality Metric Health Outcomes™ Scoring Software, version 4.5.1 or a later version and the OPTUM scoring software (Third Party vendor). In case of missingness the Full Missing Score Estimation (MSE) method or Item Response Theory (IRT) will be used, if applicable, for imputation of missing values ([Maruish, 2011](#)).

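### The SAP's HBQOL responder rule has its signs reversed: on a scale where higher is worse, a rise of 10 or more counts as improvement and a fall of 10 or more as worsening

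*SAP*

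**What the plan says.** SAP 9.1.1 maps HBQOL item levels 1 to 5 to 0, 25, 50, 75 and 100 points and averages the items within each subscale. It gives the direction as "lower scores denote less HRQoL impact, and higher scores denote more HRQoL impact (i.e., 0=best score; 100=worst score". Its worked example for the vulnerability subscale ends with a score of 50 and repeats the direction: "higher scores denote more severe negative impact of HBV on HRQOL". Protocol 8.1.2 agrees: "lower scores denote less HRQoL impact, and higher scores denote more HRQoL impact (ie, 0 best score; 100 worst score".

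SAP 9.1.2 then sets the responder rule: "Clinically important improvement = change from baseline $\geq 10$ , Clinically important worsening = change from baseline $\leq -10". All other changes count as no clinically important change. The proportions are to be calculated at each time point, by analysis phase and cohort.

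The SAP gives no definition of change that is specific to patient-reported outcomes. For the HBV markers, SAP 5.3.1.2.1 says: "Change from baseline is defined as follows: value at a given time point minus baseline value". The same convention is stated for HBV RNA and HBcrAg, for anti-HBs antibodies and for liver stiffness (SAP 5.4.1.2.1 to 5.4.1.2.3).

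**The concern.** If higher is worse and change is value minus baseline, a rise of 10 points is a deterioration, yet SAP 9.1.2 labels it improvement. A fall of 10 points, a real gain, is labelled worsening.

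The likely origin is visible in the neighbouring sections. SF-36v2 (SAP 9.2.2) and the EQ-5D VAS (SAP 9.3.2) both treat a positive change as improvement. That is right for them, because higher is better: the SF-36v2 domains run from "zero where the respondent has the worst possible health to 100 where the respondent is in the best possible health", and the VAS runs from worst at 0 to best at 100. The same sign pattern appears for HBQOL, although its scale runs the other way.

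HBQOL is the only disease-specific quality-of-life instrument in the plan, and the regimen includes interferon. Protocol 2.2.2.3 lists fatigue, anxiety and myalgia among the common adverse reactions to PegIFN-α2a. If such effects raised HBQOL scores, the responder table would report the harm as benefit. Protocol 8.1.2 also intends PGIC responses as anchors for responder analyses and for HBQOL's ability to detect change. Inverted HBQOL categories would run against that anchor.

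**Working it through.** **Inputs**

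| Input | Value | Source |
|---|---|---|
| Item scoring | levels 1–5 → 0, 25, 50, 75, 100 | SAP 9.1.1 |
| Scale direction | 0 best, 100 worst | SAP 9.1.1; Protocol 8.1.2 |
| Change | value − baseline | SAP 5.3.1.2.1 (stated for HBV markers; no rule specific to patient-reported outcomes) |
| SAP rule | improvement if change ≥ 10; worsening if change ≤ −10 | SAP 9.1.2 |
| Rule implied by the scale | improvement if change ≤ −10; worsening if change ≥ 10 | follows from the direction |

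**1. The SAP's own example.** Raw scores 2, 4 and 3 give scaled scores 25, 75 and 50. (25 + 75 + 50) / 3 = 50, as the SAP states.

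**2. Move that participant.**
- Every item one level better (1, 3, 2): (0 + 50 + 25) / 3 = 25. Change = 25 − 50 = −25. The SAP rule says worsening; the scale says improvement.
- Every item one level worse (3, 5, 4): (50 + 100 + 75) / 3 = 75. Change = 75 − 50 = +25. The SAP rule says improvement; the scale says worsening.
- One item one level better (1, 4, 3): (0 + 75 + 50) / 3 = 41.67. Change = −8.33. Both rules say no important change.
- At the extremes, 100 to 0 is labelled worsening and 0 to 100 improvement.

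**3. All possible moves on a 3-item subscale.** Scores run from 0 to 100 in steps of 25 / 3 = 8.33, which gives 13 values and 13 × 13 = 169 baseline and follow-up pairs. A change of at least 10 in size needs two steps or more. Pairs with no step number 13 and pairs one step apart number 2 × 12 = 24, so 13 + 24 = 37 fall below the threshold. The other 169 − 37 = 132 exceed it: 66 upward and 66 downward.

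| | Pairs | SAP label | Label from the scale |
|---|---|---|---|
| Change ≥ 10 | 66 | improvement | worsening |
| Change ≤ −10 | 66 | worsening | improvement |
| Otherwise | 37 | no important change | no important change |

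All 132 pairs beyond the threshold get the opposite label, and none of the 37 below it is affected. The two proportions are therefore exchanged exactly.

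**4. Effect on a table (assumed counts, not trial data).** Take 30 participants, of whom 12 fall by 10 or more and 3 rise by 10 or more. The SAP rule reports 3 / 30 = 10% improved and 12 / 30 = 40% worsened. The correct figures are 40% and 10%. The net responder difference is +30 percentage points and would be shown as −30.

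**5. Extent.** 7 subscales plus the global score make 8 scores. SAP 9.1.2 lists 5 post-baseline time points (Week 24, end of induction, end of consolidation, FU Week 24, FU Week 48). That is 8 × 5 = 40 score-by-visit results per cohort.

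**The case against.** The defect itself is hard to dispute, but its weight can be.

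- **The endpoint is exploratory.** The trial has no formal hypothesis and no formal test. SAP Table 3 schedules the quality-of-life analyses for the final analysis only, so no interim, safety or primary-efficacy result depends on them. This stands.
- **Only the proportions are wrong.** Actual values, changes from baseline and the subgroup analyses of those changes do not use the responder rule. A report with correct mean changes beside swapped proportions would show the inconsistency to a careful reader. This stands, and it limits the consequence.
- **Conflict with SF-36v2 and EQ-5D is not certain.** HBQOL covers stigma and transmission, which generic instruments need not follow. The results could disagree even if correctly signed, so the conflict is a possibility and not a prediction.
- **The change convention is not stated for patient-reported outcomes.** This is true, and the fix should state it. But neither document defines change as baseline minus value or reverse-scores HBQOL, and every convention that the SAP does state is value minus baseline.
- **A programmer might correct the sign, or the separate Data Presentation Specification might.** That specification is not among the documents. Even so, a silent correction would be an undocumented departure from the SAP.

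The protocol appendix with the HBQOL scoring instructions is redacted, but the direction is stated openly in the text of both documents.

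**Conclusion.** The rule is wrong as written. SAP 9.1.1 and 9.1.2 cannot both stand under the SAP's stated convention for change. Followed literally, 9.1.2 mislabels every participant with an HBQOL change of 10 points or more, exchanges the improved and worsened proportions for all 8 scores, and leaves the no-change proportion intact.

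This rests on two conditions: that change for patient-reported outcomes is value minus baseline, as elsewhere in the SAP, and that the rule is programmed as printed. The consequence is confined to the exploratory HBQOL responder proportions and anything built on them. The 10-point threshold is not in question.

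**What to change.** In SAP 9.1.2, define clinically important improvement as a change from baseline of −10 or less and clinically important worsening as a change of +10 or more, for all 7 subscales and the global score. Add a sentence stating that change from baseline for patient-reported outcomes is the value at the time point minus the baseline value. Leave the SF-36v2 and EQ-5D VAS rules as they are.

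Check the HBQOL responder code, any table shells and the Data Presentation Specification against the corrected text before the final analysis. The cost is two lines of SAP text and the matching code, with no effect on design, data collection or participants.

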### 9.2.1. Definition

The SF-36 is a 36-item generic PRO instrument designed to measure physical and mental health status. Participants self-report on items that have between 2-6 response options per item using Likert-type responses (e.g., none of the time, some of the time). The SF-36 is scored and interpreted using two summary scores – Physical Component Summary (PCS) and Mental Component Summary (MCS) – and eight domain subscales:

- PF: Physical functioning
- RP: Role limitations due to physical health problems
- BP: Bodily pain
- SF: Social functioning
- MH: General mental health, covering psychological distress & well-being
- RE: Role limitations due to emotional problems
- VT: Vitality, energy and fatigue
- GH: General health perceptions

Although SF-36v2 PCS and MCS scores include information from all 8 SF-36 domain subscales, the PCS score gives more weight to physical aspects of health status as represented in the Physical functioning, Physical role limitations, Pain, and General health perception domain scores. The MCS score gives more weight to the emotional and mental and social aspects of health status as assessed by the Vitality, Social function, Social role limitations, and Mental health domain scores.

A scoring algorithm will be used to convert the raw scores into the eight dimensions listed above. The total domain scores of domain scales will be transformed into a range from zero where the respondent has the worst possible health to 100 where the respondent is in the best possible health. The scores (0-100) will then be standardized using means and standard deviation from 2009 U.S. general population and converted to norm-based scores using a T-score transformation (mean = 50, SD = 10). The two component scores will be derived as linear combination of the standardized (2009 U.S. norm) scores using weights from principal component analysis. Each component score will be transformed to the corresponding PCS T-score and MCS T-score (mean = 50 and SD = 10)

The domain scale scores, and component summary scores will be calculated using the Quality Metric Health Outcomes™ Scoring Software, version 4.5.1 or a later version and the OPTUM scoring software (Third Party vendor). In case of missingness the Full Missing Score Estimation (MSE) method or Item Response Theory (IRT) will be used, if applicable, for imputation of missing values ([Maruish, 2011](#)).

### **9.2.2. Analysis Methods**

Descriptive statistics of the actual values and change from baseline values at each timepoint (including baseline and available analysis time point) for the derived PCS, MCS and 8 domain scores will be displayed by analysis phase and by cohort.

The number (and percentage) of participants with clinically important improvement/ worsening will be presented for SF-36 v2 components (PCS score, MCS score and 8 domain scores (T-scores)):

- Clinical Important Improvement = change from baseline  $\geq 5$
- Clinical Important Worsening = change from baseline  $\leq -5$ .
- Other changes from baseline values are categorized as ‘No Clinically Important Change’.

### **9.3. 5-Level EuroQol 5-Dimension Questionnaire**

#### **9.3.1. Definition**

The EQ-5D-5L questionnaire is a generic health-related quality-of-life assessment that evaluates a participant’s self-rated health state on 5 dimensions (mobility, self-care, usual activities, pain/discomfort, anxiety/depression). Additionally, a VAS records the participant’s self-rated health on a vertical VAS where the endpoints are labelled ‘best imaginable health state’ (100) and ‘worst imaginable health state’ (0).

The EQ-5D-5L questionnaire will be analyzed in 3 ways:

- EQ-5D descriptive system scores (5 scores reflecting each of the 5 dimensions).

An assessment that evaluates a subject's self-rated health state on 5 dimensions (mobility, self-care, usual activities, pain/discomfort, anxiety/depression) with 5 possible levels (no problems (level code = 1), slight problems (level code = 2), moderate problems (level code = 3), severe problems (level code = 4), extreme problems (level code = 5)).

EQ-5D VAS a continuous score ranging from 0 to 100 (with a possible range from 0 [worst imaginable health] to 100 [best imaginable health]);

This information can be used as a quantitative measure of health outcome as judged by the subject.

- EQ-5D Valuation index summarizes the information of the 5 dimensions of the descriptive system as below.

a. Assign the level code 1, 2, 3, 4 and 5 to each level of the 5 dimensions (see above)

b. Create a health state for each patient-time point combination. A health state is a combination of 5 level codes; one level code for each dimension.

E.g., health state 12543 indicates 'no problems in walking about, slight problems washing or dressing myself, unable to do my usual activities, severe pain or discomfort, moderately anxious or depressed'.

c. Assign an index value (valuation index) to each observed health state. Based on the origin of the subjects, another method can be used.

#### Missing Data:

If – for a questionnaire – one (or more) dimensions of the descriptive system are missing, then

- The EQ-5D VAS will be tabulated if not missing
- The valuation index will not be tabulated
- The non-missing dimensions of EQ-5D descriptive system will be summarized

If – for a questionnaire – the EQ-5D VAS is missing then the EQ-5D descriptive system and validation index will be tabulated if complete.

